6.12.3.1. Deaths

A listing of deaths will be provided. All deaths will be included, regardless of the Investigator's or the Sponsor's judgment about causality, including (1) any deaths occurring during participation in the study in the database for which data are being presented, (2) any deaths occurring after a patient leaves (i.e., discontinued from the study or completes the study) the study in the database for which data are being presented if the death is (a) the result of a process initiated during the study, regardless of when it actually occurs, or (b) occurs during the PTFU Period after discontinuation of study drug.

6.12.3.2. Serious Adverse Event Analyses

The number and percentage of patients who experienced an SAE will be summarized by treatment for the OLT Period (Safety Population), OLE Period (OLE Period Population and OLE Switcher Population), and LTE Period (LTE Safety Population) using MedDRA Preferred Term nested within SOC. Events will be ordered by decreasing frequency in the overall group followed in the order of ixekizumab Q4W (when applicable) then adalimumab Q2W (when applicable) group within SOC.

A follow-up emergent SAE is defined as a new SAE which occurs after the last visit during the treatment period, or an existing event worsens beyond the greatest severity reported during the PTFU Period. The baseline severity for SAEs occurring during the PTFU Period will be the maximum severity from the preceding visit before entering the PTFU Period. The number and percentage of patients who experienced a follow-up emergent SAE in the PTFU Period (PTFU Period Population) will be summarized using MedDRA Preferred Term nested within SOC. Events will be ordered by decreasing frequency in the overall group followed in the order of ixekizumab Q4W then adalimumab Q2W group within SOC.

By-patient listing of all SAEs (including death) will be provided.

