10.3.4.1. Adverse Events

Adverse events are considered TEAEs if they first occur or worsen after the start of treatment during a study period. In the case of a missing onset date for an AE, an AE with a start date equal to or greater than the dosing date will be considered a TEAE. For each TEAE, the severity is recorded according to the participant's or physician's perceived severity of the event (mild, moderate, or severe).

Treatment-emergent adverse events, SAEs including deaths, AEs that lead to investigational product discontinuation, and AEs by maximum severity and relationship to investigational product will be summarized by the Medical Dictionary for Regulatory Activities System Organ Class (SOC) and Preferred Term (PT). Treatment-emergent adverse events will also be summarized by PT sorted by decreasing frequency within SOC for all TEAEs, TEAEs by maximum severity, and TEAEs considered possibly related to study drug. For events that are gender specific, the denominator and computation of the percentage will include only participants from the given gender.

Medical Dictionary for Regulatory Activities groupings of PTs will be used to investigate AESIs.

Adverse events of special interest will also be presented by severity. Adverse events of special interest will include cytopenias, liver function test changes/enzyme elevations, infections, immunogenicity, injection site reactions, allergic/hypersensitivity reactions, cerebrocardiovascular events, malignancies, depression, IBD, and interstitial lung disease.

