6.12.2. Adverse Events

6.12.2.1. Analysis of Adverse Events

Adverse events are classified based on MedDRA. A TEAE is defined as an event that first occurred or worsened in severity after baseline and on or prior to the date of the last visit within the treatment period. Both the date/time of the event and the date/time of the dose (that is, injection) are considered when determining TEAEs. The MedDRA Lowest Level Term (LLT) will be used in the treatment-emergent computation. The maximum severity for each LLT during the baseline period will be used as baseline severity (in some cases baseline period is a single time point). Events with a missing severity during the treatment period will be considered treatment emergent. The treatment period will be included as post-baseline for the analysis. If an event is pre-existing during the baseline period but it has missing severity, and the event persists during the treatment period, then it will be considered as treatment-emergent, regardless of the post-baseline level of severity. Adverse events with a particular LLT will be classified as treatment-emergent if they first start on or after the first dose date in the treatment period (i.e., a

patient has no pre-existing conditions with that LLT), or if the severity is greater than the pre-treatment severity for that LLT.

A follow-up emergent adverse event (FEAE) is defined as an event that first occurred or worsened in severity after the date of Week 104 (Visit 29) or the ETV. The MedDRA LLT will be used when classifying FAEs as follow-up emergent. For AEs that are ongoing at the date of Week 104 (Visit 29) or ETV, the maximum severity recorded for each LLT on the date of Week 104 (Visit 29) or ETV will be used as the follow-up baseline severity for that lowest level term.

An overview table will be provided and will include the frequency and percentage of patients who experienced a TEAE, TEAE by maximum severity, a treatment-emergent AESI, SAE, died, or discontinued from the study due to an AE (including death) will be summarized by treatment group for each treatment period. A listing will be provided as well.

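### SAP 6.12.3.2: the worsening limb of the follow-up emergent SAE definition names the wrong reference period and conflicts with the sentence after it

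*SAP*

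**What the plan says.** SAP 6.12.3.2 (Serious Adverse Event Analyses) gives the rule for the post-treatment follow-up (PTFU) SAE table in two limbs and a baseline sentence.

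- New events: "A follow-up emergent SAE is defined as a new SAE which occurs after the last visit during the treatment period".
- Worsening events: "or an existing event worsens beyond the greatest severity reported during the PTFU Period".
- Baseline: "The baseline severity for SAEs occurring during the PTFU Period will be the maximum severity from the preceding visit before entering the PTFU Period".

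The same section adds a safeguard: "By-patient listing of all SAEs (including death) will be provided".

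SAP 6.12.2.1 (Analysis of Adverse Events) has the parallel rule for all AEs. The category, which the SAP abbreviates to FEAE (follow-up emergent AE) there, "is defined as an event that first occurred or worsened in severity after the date of Week 104 (Visit 29) or the ETV". For events ongoing on that date, the maximum severity recorded then for each MedDRA lowest level term "will be used as the follow-up baseline severity for that lowest level term".

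Protocol 10.3.4.1 grades severity as mild, moderate or severe. SAP 5.1 runs the long-term extension (LTE) from Week 104 (Visit 29) to Week 264 (Visit 69).

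**The concern.** A rule for worsening needs a reference fixed before the period in which worsening is judged. The second limb takes its reference from inside that period. The following sentence then supplies a pre-follow-up baseline, and the SAP does not say which of the two governs.

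At stake is the content of one table: the number and percentage of participants with a follow-up emergent SAE. The PTFU period exists to monitor safety after treatment stops. The only other PTFU event table specified in 6.12.2.1 shows FEAEs by Preferred Term, with no stated split by seriousness. If the limb were programmed as worded, an SAE ongoing at the end of treatment that became more severe in follow-up would not be counted in the SAE table.

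**Working it through.** No figure in the plan depends on this rule, so there is none to reproduce. The check is one of logic.

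**1. The limb read alone.** Let s(t) be an event's severity at time t in follow-up, and M the greatest severity reported in follow-up. The limb requires s(t) > M. By definition s(t) ≤ M for every t in follow-up, so no event satisfies it.

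**2. The baseline sentence.** Let B be the maximum severity from the visit before follow-up. Worsening then means M > B.

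**3. Enumeration.** For an event already present at entry to follow-up, three grades before and three during give 3 × 3 = 9 pairs.

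| Severity before PTFU (B) | Greatest severity in PTFU (M) | Limb read alone | Baseline sentence |
|---|---|---|---|
| mild | mild | no | no |
| mild | moderate | no | **yes** |
| mild | severe | no | **yes** |
| moderate | mild | no | no |
| moderate | moderate | no | no |
| moderate | severe | no | **yes** |
| severe | mild | no | no |
| severe | moderate | no | no |
| severe | severe | no | no |
| **Total counted** | | **0 of 9** | **3 of 9** |

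The three counted pairs are all the true worsenings. The pairs are not equally likely, so 3 of 9 is not an expected rate.

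**4. The anchor in 6.12.2.1.** FEAEs are judged from Week 104 (Visit 29) or the early termination visit (ETV). A participant who completes the LTE enters follow-up after Week 264 (Visit 69), which is 264 − 104 = 160 weeks after Visit 29. Unless ETV is stretched to cover Visit 69, neither named date is that participant's entry to follow-up. The SAE baseline sentence (visit before entry) and the FEAE baseline (Week 104/ETV) therefore differ for LTE completers.

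**The case against.** A reader might infer that SAEs worsening after treatment can never be counted, or that the probability of counting one is zero. The documents do not support that, for four reasons.

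- **The next sentence.** A baseline severity in a new-or-worsened definition has no use except to judge worsening. A programmer who applies it will count these events. This stands as evidence of intent, but it leaves two conflicting instructions in one paragraph.
- **Another parsing.** The phrase placing the comparison in the PTFU period could attach to the verb for worsening, not to the verb for reporting. The limb would then agree with the baseline sentence. The reading is possible but strained, given the word order, and a counting rule should not depend on it.
- **Other displays.** New SAEs count under the first limb whatever their severity. The worsening limb therefore mainly concerns events that were already SAEs on treatment, which appear in the treatment-period SAE tables. All SAEs are also listed by patient. This stands: no event vanishes from reporting. A listing does not, however, correct a wrong count in a table.
- **The FEAE table as a backstop.** A worsened SAE may also meet the FEAE definition, but this is uncertain. The end of 6.12.2.1 says an event already counted as treatment-emergent in the preceding treatment period is not counted again as follow-up emergent. That statement sits among the date-imputation rules, so its scope is unclear.

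**Conclusion.** The worsening limb is wrong as written and contradicts the sentence after it. Read to the letter it counts 0 of 9 severity pairs; with the SAP's own pre-follow-up baseline it counts the 3 that are worsenings. The omission occurs only if the limb is programmed literally and the baseline sentence is set aside.

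The consequence is limited to a descriptive PTFU table. The documents give no basis for estimating how many SAEs would be affected, and the number may be small. The primary analysis, the futility rule and the sample size are not touched. This is a minor drafting correction, worth making because the text is an operative counting rule for post-treatment safety.

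**What to change.** In SAP 6.12.3.2, reword the second limb along these lines: *or an existing event that worsens during follow-up beyond its baseline severity, where baseline is the maximum severity from the last visit before PTFU entry*. The separate baseline sentence then becomes part of the definition and the conflict goes.

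In SAP 6.12.2.1, use the same PTFU-entry anchor for FEAEs in place of the Week 104 (Visit 29)/ETV date, so that it also fits participants who complete the LTE.

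A maximum over all time up to entry should not be used as the anchor. Take an event that was severe early, mild at the last treatment visit and moderate in follow-up. It has worsened against the last visit (moderate > mild) but not against the any-time maximum (moderate < severe). That choice would add a third rule and drop worsenings that the SAP's baseline sentence captures.

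The cost is a few words in two SAP sections and the matching program specification. No new data are needed.

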6.12.3.3. Adverse Events Leading to Study Treatment Discontinuation

The number and percentage of patients who discontinued from the study treatment due to an AE, including patients who died, will be summarized by treatment for the OLT Period (Safety Population), OLE Period (OLE Period Population and OLE Switcher Population), and LTE Period (LTE Safety Population) using MedDRA Preferred Term nested within SOC. Events will be ordered by decreasing frequency in the overall group followed in the order of ixekizumab Q4W then adalimumab Q2W group within SOC.

Additionally, the number and percentage of patients who discontinued the study due to an AE, including patients who died, will be summarized by treatment for the PTFU Period (PTFU Period Population).

By-patient listing of AEs leading to discontinuation of study treatment will be provided.

6.12.4. Clinical Laboratory Evaluation

Laboratory evaluations will be summarized and analyzed for the following periods:

- OLT Period (Safety Population)
- OLE Period (OLE Period Population and OLE Switcher Population)
- LTE Period (LTE Safety Population), and
- Post-Treatment Follow-up Period (PTFU Period Population).

Laboratory evaluation results will be provided in a by-patient listing. Additionally, a listing of abnormal laboratory results for parameters of special interest (including laboratory analyte measurements and qualitative measures) will be provided.

Laboratory analyses will include planned analytes only. Planned analytes are those specified in the protocol. However, unplanned/unscheduled measurements of planned analytes will be included/ excluded as specified in the relevant sections. Examples of unplanned/unscheduled measurements include those that the clinical investigator orders as a repeat test or “retest” of a laboratory test if he/she has received an abnormal value, and those the investigator orders for a “follow-up visit” due to clinical concerns.

Change from baseline to last observation for laboratory tests will be summarized for patients who have both baseline and at least one post-baseline result for each treatment period. Baseline will be the last nonmissing observation in the baseline period. The last nonmissing observation in each treatment period will be analyzed. Original-scale data will be analyzed. Unscheduled visits and repeat measurements will be excluded. Box plots for observed and change values will be rendered in Spotfire. Analyses will be provided in both standard (SI) and conventional (CN) units (when different).

The number and percentages of patients with treatment-emergent abnormal, high, or low laboratory results at any time will be summarized by treatment for each treatment period. Scheduled visits, unscheduled visits, and repeat measurements will be included.

- Categorical laboratory tests:
 - A treatment-emergent **abnormal** result is defined as a change from normal at all baseline visits to abnormal at any time during the treatment period.
- Numerical laboratory tests:
 - A treatment-emergent **high** result is defined as a change from a value less than or equal to the high limit at all baseline visits to a value greater than the high limit at any time during the treatment period.
 - A treatment-emergent **low** result is defined as a change from a value greater than or equal to the low limit at all baseline visits to a value less than the low limit at any time during the treatment period.

Alanine aminotransferase (ALT), aspartate aminotransferase (AST), total bilirubin, alkaline phosphatase (ALP), neutrophils, leukocytes, platelets, and lymphocytes will not be included in this treatment-emergent abnormal, high, or low laboratory results analysis. A separate analysis to address the risk of liver injury is described in [Table RHCG.6.16](#) in which Covance reference ranges will be used.

For lower limit of normal (LLN)s of neutrophils, lymphocytes, platelets, and leukocytes, there are inconsistencies encountered for cytopenias across the large clinical trial population, Covance, and commonly accepted standard- (Wu 2006; Greer et al. 2008) based reference limits. For at least one type of cytopenia with either the large clinical trial population-based reference limits or Covance reference limits, there are certain age and gender subcategories for which the LLN is below the lower limit of the Grade 1 category as defined above, thus preventing a shift from normal to Grade 1. In order to use a set of LLNs that allow for such shifts, the LLN for the hematology parameters above will be defined by setting the LLN values using equal increments above the lower limit for Grade 1 as are defined for the incremental ranges used for Grades 2-4. This allows for equal separation of categories. Additionally, these limits are generally consistent with various commonly accepted reference limits. The only exception to this approach will be for platelets, for which the LLN will be defined as $150 \times 10^9/L$. This value is consistent with the LLNs of multiple other references ranges for platelets. Patients with neutropenia or thrombocytopenia with any grades will be categorized into 4 categories related to recovery: Recovered, Recovered with Reoccurrence, Not Recovered, and Last Visit Only. The number and percentages of patients with neutropenia and thrombocytopenia will be analyzed by grade and by recovery category.

Summaries for elevations in hepatic laboratory tests from maximum baseline category to abnormal maximum post-baseline category as well as shifts from maximum baseline to maximum post-baseline category for hepatic laboratory tests will be provided.

6.12.4.1. Leukocytes (White Blood Count [WBC]) and Platelets

Change from baseline to last observation for total leukocytes, neutrophils, platelets, lymphocytes, monocytes, eosinophils, and basophils will be summarized for patients who have both baseline and at least one post-baseline result for each treatment period. Unless otherwise specified, neutrophils will be summarized for segmented and absolute neutrophils. Baseline will be the last nonmissing observation in the baseline period. The last nonmissing observation in

each treatment period will be analyzed. Original-scale data will be analyzed. Unscheduled visits and repeat measurements will be excluded. Analyses will be provided in both SI and conventional units (when different).

Neutrophils will include both segmented neutrophils and absolute neutrophils (derived by adding segmented neutrophils and band neutrophil). The segmented neutrophils and absolute neutrophils will be summarized using the same categories.

Shift table will be produced showing the number and percentage of patients shifting from baseline to a minimum postbaseline result in each relevant category by treatment groups in the OLT, OLE, and LTE Periods:

The following LLNs will be defined for the analyses:

- Leukocytes: LLN= $4.0 \times 10^9/L$
- Neutrophils: LLN= $2.0 \times 10^9/L$
- Lymphocytes: LLN= $1.1 \times 10^9/L$
- Platelets: LLN= $150 \times 10^9/L$

Such shift tables will be produced using the following categories:

- Neutrophils: $\geq 1 \times \text{LLN}$ (Normal), $< \text{LLN}$ to $\geq 1.5 \times 10^9/L$ (Grade 1), $< 1.5 \times 10^9/L$ to $\geq 1.0 \times 10^9/L$ (Grade 2), $< 1.0 \times 10^9/L$ to $\geq 0.5 \times 10^9/L$ (Grade 3), and $< 0.5 \times 10^9/L$ (Grade 4).
- Leukocytes: $\geq 1 \times \text{LLN}$ (Normal), $< \text{LLN}$ to $\geq 3.0 \times 10^9/L$ (Grade 1), $< 3.0 \times 10^9/L$ to $\geq 2.0 \times 10^9/L$ (Grade 2), $< 2.0 \times 10^9/L$ to $\geq 1.0 \times 10^9/L$ (Grade 3), and $< 1.0 \times 10^9/L$ (Grade 4).
- Platelets: $> 1 \times \text{LLN}$ (Normal), $< \text{LLN}$ to $\geq 75.0 \times 10^9/L$ (Grade 1), $< 75.0 \times 10^9/L$ to $\geq 50.0 \times 10^9/L$ (Grade 2), $< 50.0 \times 10^9/L$ to $\geq 25.0 \times 10^9/L$ (Grade 3), and $< 25.0 \times 10^9/L$ (Grade 4).
- Lymphocytes: $\geq 1 \times \text{LLN}$ (Normal), $< \text{LLN}$ to $\geq 0.8 \times 10^9/L$ (Grade 1), $< 0.8 \times 10^9/L$ to $\geq 0.5 \times 10^9/L$ (Grade 2), $< 0.5 \times 10^9/L$ to $\geq 0.2 \times 10^9/L$ (Grade 3), and $< 0.2 \times 10^9/L$ (Grade 4).

In addition, for the above parameters (neutrophils, leukocytes, platelets, and lymphocytes), the number and percentage of patients with minimum post-baseline results will be presented overall and by treatment within the following group using the categories as defined above:

- Decreased: post-baseline category $<$ baseline category
- Increased: post-baseline category $>$ baseline category
- Same: post-baseline category $=$ baseline category

6.12.4.2. Neutrophil Follow-up

The following analyses will be conducted on the Neutrophil Follow-up Population defined as patients who have an absolute neutrophil count < 1500 cells/ μL (SI units: $< 1.5 \times 10^9/L$) at the last scheduled visit or early termination visit prior to entering the follow-up period and less than the

patient's baseline neutrophil count (that is, prior to first injection at Week 0). These patients are monitored during the follow-up period until neutrophil recovery.

Neutrophil clinical recovery is defined as an absolute neutrophil count ≥ 1500 cells/ μ L (SI units: $\geq 1.5 \times 10^9/L$) or greater than or equal to a patient's minimum neutrophil count for baseline (defined as the minimum assessment recorded on or prior to the date of first study drug injection at Week 0 [Visit 2]).

If a patient's neutrophil count has not recovered, within 12 weeks after entering the follow-up period (Visit 802), the patient will return for Visit 803 (12 weeks after Visit 802). Additional visits may be required for appropriate patient management depending upon the degree of neutropenia. If at Visit 802, a patient has met the criteria for neutrophil recovery, the patient's participation in the study will be considered complete, unless the investigator deems additional follow-up may be necessary.

The number and percentage of patients achieving neutrophil clinical recovery will be presented by dosing regimen and week interval for Neutrophil Follow-Up Population for PTFU Period. The number and percentage of patients with an absolute neutrophil cell count that is at least 25%, 50%, 75%, or 100% of the patient's baseline absolute neutrophil count (that is, prior to first injection at Week 0), irrespective of absolute neutrophil minimum, will be included in the summary.

6.12.5. Vital Signs and Other Physical Findings

Vital Signs evaluations will be summarized and analyzed for the following periods:

- OLT Period (Safety Population)
- OLE Period (OLE Period Population and OLE Switcher Population), and
- LTE Period (LTE Safety Population).

A listing of vital signs and other physical characteristics will be provided.

The planned summaries for vital signs (systolic blood pressure [BP], diastolic BP, pulse, weight, body mass index [BMI], temperature) are provided in [Table RHCG.6.13](#) and are described more fully in compound-level safety standards and in the vitals-related Pharmaceutical Users Software Exchange (PhUSE) white papers (Analyses and Displays Associated with Measures of Central Tendency – Focus on Vital Sign, Electrocardiogram, and Laboratory Analyte Measurements in Phase 2-4 Clinical Trials and Integrated Submission Documents [PhUSE 2013] and Analyses and Displays Associated with Outliers or Shifts from Normal to Abnormal: Focus on Vital Signs, Electrocardiogram, and Laboratory Analyte Measurements in Phase 2-4 Clinical Trials and Integrated Summary Documents [PhUSE 2015]).

Table RHCG.6.13. Summary Tables/Figures Related to Vital Signs

Analysis
Box plot for observed (spotfire)
Box plot for change from baseline (spotfire)
Tables with percentages of patients who shift from normal/high to low (i.e., treatment-emergent low) and percentages of patients who shift from normal/low to high (i.e., treatment-emergent high). The limits are defined in the compound-level safety standards and are based on literature.

For vital signs and physical characteristics, original-scale data will be analyzed. Mean changes from baseline and as incidence of abnormal values will be summarized.

The number and percentage of patients with treatment-emergent high blood pressure and pulse at any time for the populations mentioned in this section will be summarized. For treatment-emergent high blood pressure:

- A treatment-emergent prehypertension is defined as a change from a value less than the low limit of prehypertension at all baseline visits to a value that is within the limits of prehypertension at any time postbaseline during the treatment period.
- A treatment-emergent stage 1 hypertension is defined as a change from a value less than the low limit of stage 1 hypertension at all baseline visits to a value that is within the limits of stage 1 hypertension at any time postbaseline during the treatment period.
- A treatment-emergent stage 2 hypertension is defined as a change from a value less than the low limit of stage 2 hypertension at all baseline visits to a value that is greater than or equal to the limits of stage 2 hypertension at any time postbaseline during the treatment period.

For treatment-emergent high or low value in pulse rate:

- A treatment-emergent high value is defined as a change from a value less than or equal to the high limit at all baseline visits to a value greater than the high limit at any time postbaseline during the treatment period.
- Treatment-emergent low value is defined as a change from a value greater than or equal to the low limit at all baseline visits to a value less than the low limit at any time postbaseline during the treatment period.

[Table RHCG.6.14](#) provides the blood pressure levels for children by age and gender and [Table RHCG.6.15](#) provides the criteria for abnormal treatment-emergent pulse rate in children and adolescents by age and gender.

Table RHCG.6.14. Blood Pressure Levels for Children by Age and Gender (Median Height)

Age (Year)	Hypertension Stage	Boy		Girl	
		Systolic BP (mmHg) (supine or sitting – forearm at heart level)	Diastolic BP (mmHg) (supine or sitting – forearm at heart level)	Systolic BP (mmHg) (supine or sitting – forearm at heart level)	Diastolic BP (mmHg) (supine or sitting – forearm at heart level)
6	Prehypertension	≥110 and <114	≥70 and <74	≥108 and <111	≥70 and <74
	Stage 1	≥114 and <126	≥74 and <87	≥111 and <124	≥74 and <86
	Stage 2	≥126	≥87	≥124	≥86
7	Prehypertension	≥111 and <115	≥72 and <76	≥109 and <113	≥71 and <75
	Stage 1	≥115 and <127	≥76 and <89	≥113 and <125	≥75 and <87
	Stage 2	≥127	≥89	≥125	≥87
8	Prehypertension	≥112 and <116	≥73 and <78	≥111 and <115	≥72 and <76
	Stage 1	≥116 and <128	≥78 and <91	≥115 and <127	≥76 and <88
	Stage 2	≥128	≥91	≥127	≥88
9	Prehypertension	≥114 and <118	≥75 and <79	≥113 and <117	≥73 and <77
	Stage 1	≥118 and <130	≥79 and <92	≥117 and <129	≥77 and <89
	Stage 2	≥130	≥92	≥129	≥89
10	Prehypertension	≥115 and <119	≥75 and <80	≥115 and <119	≥74 and <78
	Stage 1	≥119 and <132	≥80 and <93	≥119 and <131	≥78 and <91
	Stage 2	≥132	≥93	≥131	≥91
11	Prehypertension	≥117 and <121	≥76 and <80	≥117 and <121	≥75 and <79
	Stage 1	≥121 and <134	≥80 and <93	≥121 and <133	≥79 and <92
	Stage 2	≥134	≥93	≥133	≥92
12	Prehypertension	≥120 and <123	≥76 and <81	≥119 and <123	≥76 and <80
	Stage 1	≥123 and <136	≥81 and <94	≥123 and <135	≥80 and <93
	Stage 2	≥136	≥94	≥135	≥93
13	Prehypertension	≥120 and <126	≥77 and <81	≥120 and <124	≥77 and <81
	Stage 1	≥126 and <138	≥81 and <94	≥124 and <137	≥81 and <94
	Stage 2	≥138	≥94	≥137	≥94
14	Prehypertension	≥120 and <128	≥78 and <82	≥120 and <126	≥78 and <82
	Stage 1	≥128 and <141	≥82 and <95	≥126 and <138	≥82 and <95
	Stage 2	≥141	≥95	≥138	≥95
15	Prehypertension	≥120 and <131	≥79 and <83	≥120 and <127	≥79 and <83
	Stage 1	≥131 and <143	≥83 and <96	≥127 and <139	≥83 and <96
	Stage 2	≥143	≥96	≥139	≥96
16	Prehypertension	≥120 and <134	≥80 and <84	≥120 and <128	≥80 and <84
	Stage 1	≥134 and <146	≥84 and <97	≥128 and <140	≥84 and <96
	Stage 2	≥146	≥97	≥140	≥96
17	Prehypertension	≥120 and <136	≥80 and <87	≥120 and <129	≥80 and <84
	Stage 1	≥136 and <148	≥87 and <99	≥129 and <141	≥84 and <96

Age (Year)	Hypertension Stage	Boy		Girl	
		Systolic BP (mmHg) (supine or sitting – forearm at heart level)	Diastolic BP (mmHg) (supine or sitting – forearm at heart level)	Systolic BP (mmHg) (supine or sitting – forearm at heart level)	Diastolic BP (mmHg) (supine or sitting – forearm at heart level)
	Stage 2	≥148	≥99	≥141	≥96

Abbreviations: BP = blood pressure; mmHg = millimeters of mercury. Source: [NIH 2005] The Fourth report on the Diagnosis, Evaluation, and Treatment of High Blood Pressure in Children and Adolescents. Revised May 2005

Table RHCG.6.15. Categorical Criteria for Abnormal Treatment-Emergent Pulse Rate in Children and Adolescents Requiring Evaluation and Potential Intervention by a Health Care Professional Pressure Levels for Children by Age and Gender (Median Height)

Parameter	Age (year)	Low	High
Pulse (bpm) ^a	6 - 9	<60	>150
	10 - 11	<60	>140
	12 - 14	<50	>120
	15 - 17	<50	>100

Abbreviations: bpm = beats per minute. Source: See the Selected Reference Limits for Pulse/Heart Rate, Arterial Blood Pressure [Including Orthostasis], and Electrocardiogram Numerical Parameters for Use in Analyses of Phase 2-4 Clinical Trials guidance, located on the CV SAC Collaboration site.

^a Baseline abnormal values are defined by the value presented.

